1 PROTOCOL SUMMARY

1.1 SYNOPSIS

Title: A Single-Site, Parallel-Group, Randomized-Controlled Trial of Navigation Versus Usual Care for The Management of Delays and Racial Disparities Starting Postoperative Radiation Therapy in Adults with Surgically-Managed, Locally Advanced Head and Neck Squamous Cell Carcinoma (NDURE 2.0)

Grant Number: K08CA237858-01A1

Study Description: In this study, we evaluate the feasibility, acceptability, preliminary clinical impact, and preliminary behavioral impact of NDURE (Navigation for Disparities and Untimely Radiation thErapy), a multi-level, theory-based navigation intervention to improve timely, equitable post-operative radiation treatment (PORT) among patients with Head and Neck Squamous Cell Carcinoma (HNSCC). We hypothesize that NDURE will be feasible, acceptable, improve the timeliness of PORT for white and African American (AA) HNSCC patients and decrease disparities in delay between the two groups by improving system-, interpersonal-, and individual-level health behavior constructs.

Objectives:Primary Objective (NDURE feasibility study):

1. To assess the feasibility of NDURE among white and AA HNSCC patients.

Secondary Objectives (NDURE feasibility study):

1. To assess the acceptability of NDURE to white and AA HNSCC patients and providers.
2. To determine the feasibility of a single dedicated navigator to manage a caseload of patients for the NDURE intervention
3. To evaluate the feasibility of collecting pre- and post-NDURE intervention outcome measures in this patient population

Primary Objective (RCT of NDURE vs Usual Care):

1. To evaluate the preliminary clinical impact of NDURE compared with usual care (UC) on delays starting PORT among white and AA HNSCC patients.

Secondary Objectives (RCT of NDURE vs Usual Care):

1. To evaluate the preliminary clinical impact of NDURE compared with UC on racial disparities in delays starting PORT among white and AA HNSCC patients.
2. To assess the preliminary clinical impact of NDURE compared with UC on barriers to care
3. To determine the preliminary impact of NDURE compared with UC on cancer care delivery processes.
4. To evaluate the preliminary behavioral mechanism of action of NDURE.

Endpoints:Primary Endpoint:

PORT Delay

Secondary Endpoints:

NDURE Accrual Rate

NDURE Completion Rate

Navigation Session Completion Rate

Questionnaire Completion Rate

Navigator Caseload

Navigator Time Allocation (Direct)

Navigator Time Allocation (Indirect)

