the neck are staged (i.e. occur on two different calendar days), the date of the definitive surgery for the primary tumor will be used. In situations in which an additional surgical resection is required (e.g. re-resection of positive margins to clear residual disease), the date of the earlier (i.e. attempted definitive) surgical procedure will be used to determine the date of definitive surgical resection.

Time-to-PORT (TTP) is defined as the time, in days, between the date of definitive surgical resection to the initiation of PORT. All of the criteria used to adjudicate the date of the definitive surgical procedure described for the primary outcome measure will be applied to this measure.

Barriers to Care

Rate of barrier resolution is defined as the proportion of confirmed barriers (as determined by the navigator log) that are resolved during the NDURE intervention.

Unresolved barriers are the number of confirmed barriers (as determined by the navigator log) that are not resolved during the NDURE intervention.

Cancer Care Delivery Processes

Pre-Surgical Radiation Consultation is defined as the attendance by the patient at a consultation with a radiation oncologist (at MUSC or elsewhere) prior to surgery to discuss RT in the definitive or adjuvant setting

Pre-Radiation Therapy Dental Extractions is defined as the extraction of teeth prior to discharge from the index hospitalization for the definitive surgical procedure. Patients who are edentulous are not evaluable for this measure.

Surgery to Pathology Report <= 7 days is defined as the production of the pathology report from the definitive surgical procedure within the EMR within 7 calendar days of the definitive surgical procedure. Addenda to the pathology report at the request of the HNSCC team (e.g. tumor p16 status) are not counted in this measure.

Surgery to PORT Referral <= 10 days is defined as the placement of a referral for PORT, at MUSC or elsewhere, within 10 calendar days of the definitive surgical procedure.

RT Referral to Consult <= 10 days is defined as the evaluation of the patient at a postoperative consultation with a radiation oncologist within 10 calendar days of the referral being placed (or postoperative appointment being scheduled in cases in which care has been established and the return visit is no longer a consultation). The consultation may occur in the clinic or the hospital depending upon clinical circumstances.

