Change from baseline in Communication & Attitudinal Self-Efficacy Scale (CASE)-Cancer score is defined as the change in CASE-Cancer Score from baseline. The CASE-Cancer is a validated, psychometrically sound 12-item scale that addresses three domains of self-efficacy in cancer care (understanding and participating in care, maintaining a positive attitude, and seeking and obtaining information)⁵³. The CASE-Cancer scale has been used extensively in PN studies to measure perceived self-efficacy^{10,44,52}. Responses are on a 4-point Likert scale from 'Strongly disagree' (1) to 'Strongly Agree' (4). Higher scores indicate greater levels of self-efficacy in cancer care.

Navigator Barrier Log will measure 1) the number of barriers identified in the BRP during NDURE; and 2) the type of barrier in our modified version of existing PN logs^{11,44,51}

Covariates

Behavioral Risk Factor Surveillance Survey (BRFSS) Demographics. The BRFSS is the nation's premier health-related survey that collects data about health-related risk behaviors from US residents. The demographic section from the BRFSS will be used (in-person) to ascertain participant sex, age, race,

marital status, insurance, educational attainment, living situation, zipcode, phones for personal use, employment, and annual household income⁵⁴.

BRFSS Tobacco Use and Alcohol Consumption. The tobacco use and alcohol consumption sections of the BRFSS will be used (in-person) to characterize total cigarette exposure, current cigarette use, quit attempts, days of alcohol consumption, average drinks/day, frequency of ≥ 5 drinks, and maximum number of drinks.

Clinical and Oncologic Characteristics. Clinical characteristics will include comorbid medical conditions (as defined by the ACE-27⁵⁵, which ranks the severity of each of a patient's comorbidities from 0-3 and gives an overall comorbidity score based on the patient's highest comorbidity score for any individual type of ailment, with 3 indicating severe comorbidity) and cancer history. Oncologic characteristics will include HNSCC tumor subsite, HNSCC tumor histology, p16/human papillomavirus (HPV) tumor status, American Joint Committee on Cancer TNM Class and overall stage grouping, type of ablative surgery, type of reconstruction, treatment dates, facility of planned adjuvant therapy, and adjuvant treatment type planned (adjuvant radiation or chemoradiation).

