Cultural Factor Survey Scores is reported as the total score for each of the three individual subscales. The Cultural Factor Survey is a validated, psychometrically sound questionnaire consists of three subscales assessing temporal orientation (5 items), collectivism (6 items), and religiosity (9 items)⁵⁶. Prior PN studies have used these scales to measure cultural factors⁵⁷. Items are scored on a 4-point Likert scale from 'Strongly Disagree' (1) to 'Strongly Agree' (4). Scores on each sub-scale range from 5-20 (temporal orientation), 6-24 (collectivism), and 9-36 (religiosity). Higher scores on each subscale indicate greater amounts of each of the measured construct.

PORT Nomogram is a validated risk-prediction tool to estimate a personalized pre-treatment risk of PORT delay⁵⁸.

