9.4.3.2 RCT OF NDURE VERSUS USUAL CARE

We will analyze the secondary endpoint of TTP as a continuous variable and estimate median time to PORT for each arm and for racial subgroups within each arm using Kaplan-Meier curves with Greenwood variance estimation to construct the corresponding 95% CIs. Hazard ratio comparing the two arms will be estimated using Cox proportional hazards regression controlling for the stratification variables. TTP will be compared between intervention arms using a stratified log-rank test on the modified ITT efficacy analysis population.

For the secondary endpoints of barrier reduction and unresolved barriers, we will calculate the proportion of unresolved barriers and the frequency of unresolved barriers (respectively) at the end of NDURE, consistent with prior PN studies⁵¹. We will use logistic regression to assess the relationship between unresolved barriers and the rate of PORT delay (primary endpoint), controlling for covariates listed in **Section 8.1**.

For other secondary endpoints, data will be summarized using frequency and percent for categorical variables and using mean, median, standard deviation, IQR and range for continuous variables. We will construct 95% CIs to provide a measure of uncertainty in estimated proportions and means. Comparisons between trial arms of other secondary endpoints will be performed using *t*-tests and chi-square tests, or Wilcoxon rank sum and Fisher's exact tests as appropriate. Pre- and post-intervention values of variables measuring the theoretical constructs underlying NDURE (i.e. care coordination, self-efficacy in cancer care, support, and knowledge) will be compared using Wilcoxon sign rank tests. Comparisons between arms of the change in scores will be conducted using Wilcoxon rank sum tests. All secondary endpoint

will be analyzed on the modified ITT efficacy analysis population. Missing data will be handled as described in **Section 9.4.2.2, RCT of NDURE Versus Usual Care**.

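### The barrier regression in Section 9.4.3.2 adjusts for an unselected list of about 34 covariates, and the documents do not settle which arms supply its barrier count

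*Combined protocol and SAP*

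**What the plan says.** **The model.** Section 9.4.3.2 plans a "logistic regression to assess the relationship between unresolved barriers and the rate of PORT delay (primary endpoint), controlling for covariates listed in" Section 8.1. Section 8.1 has a block headed Covariates covering demographics, tobacco and alcohol use, clinical and oncologic characteristics, cultural scores and a nomogram. One stretch of it reads "treatment dates, facility of planned adjuvant therapy", and it ends with "PORT Nomogram is a validated risk-prediction tool to estimate a personalized pre-treatment risk of PORT delay". Section 9.4.1 promises pre-specified covariates later in the text, but no shorter list, selection rule or penalisation follows.

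**The barrier endpoints.** Secondary objective 2 of the RCT is "To assess the preliminary clinical impact of NDURE compared with UC on barriers to care" (Section 1.1, repeated in Section 3). Section 8.1 defines barrier resolution as the "proportion of confirmed barriers (as determined by the navigator log) that are resolved during the NDURE intervention" and unresolved barriers as "the number of confirmed barriers (as determined by the navigator log) that are not resolved during the NDURE intervention". The log itself records "the number of barriers identified in the BRP during NDURE". Section 9.4.3.2 takes the barrier measures when NDURE ends, and says that all secondary endpoints "will be analyzed on the modified ITT efficacy analysis population", which contains both arms (Section 9.3). Section 6.1.2.2 says that usual care has no dedicated interventionist. The schedule in Section 1.3 is one table for both arms and puts no arm restriction on its barrier rows.

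**The concern.** A logistic model with far more covariates than the events can carry either has no finite solution or gives exaggerated estimates with tests that reject too often. This is the only planned analysis that links barriers to delay, so it would be read as evidence on how navigation works.

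The arm question decides which failure occurs. It also decides whether secondary objective 2 has a contrast on its own endpoints. The between-arm tests in Section 9.4.3.2 are assigned to the other secondary endpoints, so none is named for barrier resolution or unresolved barriers.

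**Working it through.** **1. The plan's own figure.** Section 9.2.2 gives 83% power for 75 per arm, 45% versus 25%, two-sided alpha 0.1. Pooled SE = √(0.35 × 0.65 × 2/75) = 0.0779. Unpooled SE = √((0.45 × 0.55 + 0.25 × 0.75)/75) = 0.0762. Power = Φ((0.20 − 1.645 × 0.0779)/0.0762) = 82.7%. This agrees, so the same rates are used for the event counts.

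**2. Covariates named in Section 8.1.**

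| Block | Variables |
|---|---|
| Demographics | 11 |
| Tobacco and alcohol | 7 |
| Comorbidity, cancer history | 2 |
| Oncologic | 10 |
| Cultural subscales | 3 |
| Nomogram | 1 |
| **Total** | **34** |

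The count is 33 if TNM class and stage are one item, and 36 if T, N and M are separate. It understates the number of parameters, because zipcode, subsite and other categorical items need several columns each.

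**3. Events per covariate.** NDURE only: 0.25 × 75 = 18.75 delays; 18.75/34 = 0.55. Both arms: 18.75 + 0.45 × 75 = 52.5 delays; 52.5/34 = 1.54. If NDURE had no effect and delay were 45% in both arms, the figures with the barrier term counted would be 33.75/35 = 0.96 and 67.5/35 = 1.93.

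**4. Simulation.** There were 2,000 runs per cell, with 75 patients per arm and delay of 25% and 45%. Assumptions that are not in the documents: unresolved barriers Poisson with mean 1, covariates independent of outcome, one column each. Treatment dates were removed, leaving 33 covariates. Monte Carlo error on the false-positive rates is about 0.5 to 0.6 points.

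- *NDURE only, 33 covariates:* 77.1% of datasets separate at a true odds ratio (OR) of 1.0, and 83.6% at 1.5. With 3 covariates none separate, and the median OR is 1.53 for a true 1.5.
- *Both arms:* no separation.

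| Both arms | Median OR (true 1.5) | False positives (true 1.0) |
|---|---|---|
| 33 covariates, no arm term | 1.70 | 8.1% |
| 33 covariates, with arm | 1.80 | 8.7% |
| 3 covariates, no arm term | 1.48 | 4.2% |
| 3 covariates, with arm | 1.54 | 5.0% |

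Repeats with other seeds gave 78 to 84% separation for NDURE only. For both arms with an arm term and 33 covariates they gave medians of 1.74 to 1.81 and false positives of 8.7 to 9.3%. At a true OR of 1.0 the 33-covariate median was 1.00.

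**5. Treatment arm.** Arm is not in the Section 8.1 list. If both arms enter and NDURE lowers barriers as well as delay, leaving arm out creates an association. With no barrier effect and 3 covariates, assumed means of 0.8 (NDURE) and 1.2 (usual care) give OR 1.09 and 7.8% false positives without arm, against 1.00 and 4.6% with it. Means of 0.6 and 1.4 give 1.17 and 16.8%, against 0.99 and 5.4%.

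**6. Treatment dates.** PORT delay is computed from the surgery date and the PORT start date. With both in the model, 300 of 300 simulated datasets separate, as they must. With the surgery date alone, none do.

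**7. Timing of the barrier count.** Section 6.1.1.1 has the navigator tracking barriers until PORT starts, and Section 9.4.3.2 takes the count when NDURE ends. The count therefore closes when the outcome is settled, and a patient who starts late has a longer window. A shorter covariate list does not cure this.

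**The case against.** The Covariates block can be read as a catalogue of what is collected, not a model specification. No analyst would enter zipcode and every alcohol item, so the 34-variable model is the worst-case reading. That is fair. But the cross-reference points at that block, and nothing in the plan selects from it.

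The simulations rest on an invented barrier distribution and effect size. That also stands. The exact percentages are illustrative, but the ratio of events to covariates comes from the documents' own figures.

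Three stronger conclusions are tempting and are not supported:

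- A reader might infer that usual-care patients will have no barrier data. The definitions point that way, but the schedule covers both arms without restriction and the analysis population has both. No section says who would confirm or log barriers in usual care. The documents conflict; they do not rule the data out.
- A reader might infer that treatment dates make the model degenerate. That holds only if both the surgery and PORT start dates are entered, and Section 8.1 does not say which dates are meant.
- A reader might infer that the trial has no between-arm evidence on barriers. Change in the Perceived Barriers measure is already an RCT endpoint (Section 3), and Section 9.4.3.2 plans Wilcoxon rank sum comparisons of change scores. It is self-reported and sits under the behavioural-mechanism objective, so it is not the log endpoint of objective 2.

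**Conclusion.** The concern holds for one secondary association model and for the definition of the objective 2 endpoints. Read as written, the regression has about 0.55 or 1.5 events per covariate. Under the stated assumptions, about 77 to 84% of NDURE-only fits have no finite estimate. With both arms, false positives are about 8 to 9% and a true OR of 1.5 is estimated at about 1.7 to 1.8.

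The exaggeration applies only when a barrier effect exists. Under no effect the median is not biased, and the harm is the excess of false positives. The arm question is a contradiction between sections that must be reconciled, not proof that data are missing. The primary Mantel-Haenszel comparison is unaffected.

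**What to change.** **Covariates.** Replace the reference to Section 8.1 with a short pre-specified baseline set, for example race and planned radiation facility (the strata of the primary test). Add nomogram risk if it does not duplicate them; Section 8.1 does not list its inputs. Exclude treatment dates. Add treatment arm if both arms enter. Label the model exploratory. With three covariates this gives 18.75/4 = 4.7 events per coefficient (NDURE only) or 52.5/5 = 10.5 (both arms, with arm).

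**Timing.** State that unresolved barriers are counted up to PORT start. Either use the count at a fixed earlier visit, such as the already scheduled Visit 4, or report the association as descriptive.

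**Arms.** State which arms have log barrier data and, if usual care does, who records them. If only NDURE does, report the log endpoints as NDURE-only description and take the between-arm evidence for objective 2 from the Perceived Barriers change score. Name that score explicitly in Section 9.4.3.2, because the constructs listed beside the Wilcoxon tests do not include it. State its scoring and visit, and say that it measures a different, self-reported construct.

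**Cost.** These are wording changes, since the variables are already collected. Fewer confounders are adjusted for in an observational association, and a Visit 4 count misses later barriers. Power stays limited and depends on the barrier distribution. For an OR of 1.5 with both arms and an arm term it is about 64% at Poisson mean 1 (62% in a repeat), 38% at mean 0.5 and 96% at mean 3. For NDURE only it is about 33% at mean 1.

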4.2 RCT OF NDURE VERSUS USUAL CARE

4.2.1 OVERALL DESIGN

We will conduct a single-site, non-blinded, parallel-group, RCT of NDURE versus usual care for the management of delays and racial disparities starting PORT in adults with surgically-managed, locally advanced HNSCC. The study is designed to test the following hypotheses: 1) NDURE will result in a lower rate of delayed PORT relative to usual care (primary objective) and 2) NDURE will result in a smaller difference in PORT delay between AA and whites relative to usual care (secondary objective). The statistical plan for this between-group design analyzes the superiority of NDURE relative to usual care, although our power analysis is calculated with $\alpha = 0.1$ and $1 - \beta = 0.8$ based on the desire to emphasize power over type I error at this early stage of development (single-site pilot RCT) to ensure follow-up on promising interventions.

Upon enrollment and completion of the baseline assessments, patients will be randomized 1:1 to NDURE or usual care using a permuted block randomization method, with randomly selected block sizes of 2 or 4. Randomization, which will occur at the individual patient level, will be stratified with a 1:1 allocation ratio with strata defined by race (white, AA) and location of radiation facility (MUSC, non-MUSC) because of the known association of these variables with PORT delay^{6,33}. Furthermore, to facilitate evaluation of PORT delay rates in racial subgroups, we will oversample AAs for a final sample size of 50 white and 25 AA patients in each arm (see details in **Section 9.4.6, Sub-Group Analyses**). Given the impossibility of delivering the NDURE intervention in a non-blinded fashion, allocation concealment will be non-blinded. The study statistician ([name]) will generate the randomization schema and

randomization list. The study coordinator will implement the randomization. Randomization errors will be handled as per the modified intention-to-treat (ITT) population for the efficacy analysis.

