6.3 MEASURES TO MINIMIZE BIAS: RANDOMIZATION AND BLINDING

Bias will be minimized through stratified sampling and a stratified randomized permuted block design. We will use a stratified sampling approach to achieve a fixed sample size for AA patients (n=25 in each arm) to ensure that we 1) achieve racial balance between the NDURE and UC arms, and 2) oversample AA relative to their frequency in the study population. Oversampling AAs is key for the study design because of the prognostic significance of AA race with delayed PORT initiation^{6,33}. We will then use a stratified randomization scheme, with randomization at the individual patient level using a 1:1 allocation ratio. Strata will be defined by location of radiation facility (MUSC, non-MUSC) because of the known association of this variable with PORT delay^{6,33}. As such, our design balances by key potential confounders across trial arms. Patients will be randomized 1:1 to NDURE or usual care using a permuted block randomization method, with randomly selected block sizes of 2 or 4. Given the impossibility of delivering the NDURE intervention in a non-blinded fashion, allocation concealment will be non-blinded. The study statistician ([name]) will generate and implement the randomization schema and randomization list. The study coordinator will implement the randomization. Randomization errors will be handled as per the modified ITT population for the efficacy analysis (see **Section 9.3, Population for Analyses**).

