9.2.2 RCT OF NDURE VERSUS USUAL CARE

Power and sample size calculations were performed using PASS v08.0.13, “Inequality Tests for Two Independent Proportions.” The primary endpoint for this pilot RCT is the rate of PORT delay, defined as starting PORT > 6 weeks after surgery. Our primary objective is to compare PORT delay rates between the NDURE and usual care arms. We hypothesize that, compared with patients who receive usual care, patients who receive NDURE will have a decreased rate of PORT delay (initiation of PORT > 6 weeks after surgery). Alternatively, our null hypothesis is that there will be no difference in the rate of PORT delay between NDURE and usual care. We assume the rate of PORT delay in the usual care arm will be 45%³³ and target an absolute reduction in PORT delay of 20% (rate of PORT delay in the NDURE arm = 25%)²⁴. This effect size is clinically significant and realistic given results in similar (non-randomized) interventions²⁴. Seventy-five patients in each arm yields 83% power to detect a 20% reduction in PORT delay (45% versus 25%) based on a two-sided Mantel-Haenszel test of two independent proportions assuming a two-sided $\alpha = 0.1$. Our choice of the Mantel-Haenszel test to compare proportions is based on the trial’s stratified design. Our selection of $\alpha = 0.1$ and $1 - \beta = 0.8$ is based on the desire to emphasize power over type I error at this early stage of development (single-site pilot RCT) to ensure follow-up on promising interventions. We therefore consider our RCT to be appropriately and rigorously designed to detect a clinically meaningful reduction in PORT delay. In order to have 150 patients eligible for the

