9.4.2.2 RCT OF NDURE VERSUS USUAL CARE

For the primary endpoint (delays starting PORT as defined in **Section 8.1, Endpoint and Other Non-Safety Assessments**), we will calculate the percentage of patients who start PORT > 6 weeks after surgery and corresponding 95% confidence interval (CI) for both arms and for white and AA subgroups within each arm in the efficacy analysis population. The rate of PORT delay will be compared between arms using a Mantel-Haenszel test of two proportions, with strata defined by race and location of radiation facility.

Every effort will be made to minimize missing data and lost-to-follow-up participants. Participants will complete assessments at baseline and post intervention using an iPad-based REDCap collection method. The program coordinator will attempt to contact patients at least three times using a variety of methods of communication (e.g. text message, phone call, email, mail, etc) to complete outcome measures. This method resulted in 100% instrument completion in prior studies conducted by our team.

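### Care-process endpoints, CTM-15 and change scores are compared by unstratified tests in a stratified trial: valid, but less efficient to the extent that race or radiation facility predicts the endpoint

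*Combined protocol and SAP*

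**What the plan says.** Section 4.2.1 says that randomisation "will be stratified with a 1:1 allocation ratio with strata defined by race (white, AA) and location of radiation facility (MUSC, non-MUSC". Section 6.3 describes it differently. There race is handled by stratified sampling, with 25 AA patients fixed in each arm, and for the randomisation itself: "Strata will be defined by location of radiation facility (MUSC, non-MUSC) because of the known association of this variable with PORT delay".

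The primary endpoint follows the design. Section 9.4.2.2 compares PORT delay "using a Mantel-Haenszel test of two proportions, with strata defined by race and location of radiation facility". Section 9.2.2 begins its explanation "Our choice of the Mantel-Haenszel test to compare proportions is based on the" and names the stratified design as the basis. In 9.4.3.2, time to PORT has a stratified log-rank test and a Cox model that controls for the stratification variables.

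Later in 9.4.3.2 the strata drop out. For the remaining secondary endpoints: "Comparisons between trial arms of other secondary endpoints will be performed using *t*-tests and chi-square tests", or rank-sum and Fisher's exact tests where appropriate. These endpoints include the six binary care-process measures and CTM-15. For the questionnaires: "Comparisons between arms of the change in scores will be conducted using Wilcoxon rank sum tests". No reason is given for the change of approach.

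**The concern.** When allocation is balanced within strata and a stratum predicts the outcome, the difference between arms varies less than an unstratified test assumes. The test then rejects too rarely under the null and loses power. The secondary objective on cancer care delivery processes is answered by such tests.

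The plan says that this pilot favours power over type I error (4.2.1, 9.2.2), so giving up power without a stated reason runs against its own aim. The process results would also be on a different basis from the primary result that they are meant to help explain.

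**Working it through.** **1. The plan's own figure.** The only stated power is for PORT delay: 75 per arm, 45% against 25%, two-sided alpha 0.1 (9.2.2). The pooled proportion is 0.35.
- Standard error under the null: √(2 × 0.35 × 0.65 / 75) = 0.0779.
- Standard error under the alternative: √((0.45 × 0.55 + 0.25 × 0.75) / 75) = 0.0762.
- Power: Φ((0.20 − 1.645 × 0.0779) / 0.0762) = Φ(0.94) = 82.7%, which matches the stated 83%.

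No power or effect size is planned for the endpoints at issue. The steps below use two-sided alpha 0.05 (9.4.1) and assumed effects.

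**2. Formula.** Let R² be the share of outcome variance explained by the strata. With 1:1 allocation within strata, the unstratified z statistic has null variance of about 1 − R².
- True alpha = 2[1 − Φ(1.96 / √(1 − R²))].
- Unstratified power, where the stratified test has 80%, = Φ(1.96 + 0.84 − 1.96 / √(1 − R²)).

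For R² = 0.10, 1.96 / √0.90 = 2.066. Alpha is 3.9% and power is Φ(2.80 − 2.066) = 76.9%.

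| R² | Unstratified alpha | Unstratified power | Gain from stratifying (points) |
|---|---|---|---|
| 0 | 5.0% | 80.0% | 0 |
| 0.014 | 4.8% | 79.6% | 0.4 |
| 0.05 | 4.4% | 78.5% | 1.5 |
| 0.10 | 3.9% | 76.9% | 3.1 |
| 0.20 | 2.8% | 72.9% | 7.1 |

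The only stratum effect with a stated size is race on PORT delay: AA patients are 31% more likely to be delayed (2.2.2). I read this as a relative risk (an assumption), at 45% overall with one third AA. The white rate is then 0.45 / (2/3 + 1.31/3) = 40.8%, the AA rate is 53.4%, and the gap is 12.6 points. For a binary endpoint near 50%, R² = 0.126² × (1/3)(2/3) / 0.25 = 0.014. If a process endpoint had that race effect and no facility effect, the loss would be 0.4 points.

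**3. Simulation of the design.** 170 patients are randomised in four strata with blocks of 2 or 4, and 20/170 = 12% are removed at random to reach about 150. The facility split is 50:50 (assumed), the endpoint is near 50%, and the arm difference is 22.5 points. Each cell gives chi-square / Mantel-Haenszel.

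| Race gap | Facility gap | R² | Type I error | Power |
|---|---|---|---|---|
| 0 | 0 | 0 | 5.1% / 5.1% | 79.0% / 78.7% |
| 12.6 | 0 | 0.014 | 4.9% / 5.0% | 80.0% / 80.1% |
| 12.6 | 15 | 0.04 | 4.8% / 5.2% | 80.4% / 81.2% |
| 12.6 | 30 | 0.10 | 4.2% / 5.1% | 80.2% / 83.6% |
| 20 | 40 | 0.20 | 3.3% / 5.1% | 81.6% / 87.6% |

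**4. Facility effect alone.** 75 per arm, half at each facility, common log odds ratio 0.95. Ranges are over repeat runs; each cell gives chi-square / Mantel-Haenszel.

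| Usual-care success, MUSC vs non-MUSC | Type I error | Power |
|---|---|---|
| 60% vs 50% | no material difference | no material difference |
| 70% vs 40% | 4.5–4.6% / 5.0% | 72% / 74–75% |
| 80% vs 40% | 3.5–3.7% / 5.0–5.1% | 63% / 69–70% |
| 85% vs 35% | 2.5–2.7% / 5.0–5.1% | 55–56% / 66–67% |

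The simulated chi-square errors sit slightly above the formula because the counts are discrete. The direction and order of size agree.

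**5. Scores.** Simulated power for a continuous score, t-test against stratum-adjusted linear model: R² 0, 80.1% / 80.3%; R² 0.04, 78.8% / 79.9%; R² 0.11, 76.4% / 79.3%; R² 0.23, 71.1% / 80.1%.

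**6. Which endpoints could be affected.** By the definitions in 8.1, referral to consult and consult to initiation are radiation-oncology steps of the surgery-to-PORT interval. A facility factor associated with the whole interval plausibly acts through one of them. The pathology report and the dental extractions are measured around surgery at MUSC, and no route from the later radiation site is apparent. For the pre-surgical consultation, the PORT referral, CTM-15 and the change scores, the documents state no link.

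**The case against.** The strongest reply is that nothing here is invalid. Any error is conservative, these are unpowered secondary endpoints of a pilot, and the primary result is untouched. All of that stands.

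It also stands that the documents support the strata as predictors of PORT delay only: "because of the known association of these variables with PORT delay". A reader might infer that the unstratified tests certainly lose power on all these endpoints, or that the loss is around 10 points. The documents support neither. The larger gains need facility gaps of 40 to 50 points, for which they give no basis. The 51% of cases with transitions across healthcare systems (2.2.5) comes from the reference that 4.2.4 calls national historical data. It is not this site's facility split.

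A reader might also infer that the planned confidence intervals are too wide. Section 9.4.3.2 plans intervals for proportions and means and names none for a between-arm difference, which is the only kind that stratification would narrow. Finally, Fisher's exact test has a use for small counts, for example dental extractions, where edentulous patients are not evaluable.

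What the reply does not supply is a reason to leave the strata out. The plan's stated basis for Mantel-Haenszel, the stratified design, applies equally to the binary process endpoints. Stratifying where the strata predict nothing cost at most about 0.3 points of power in the simulations.

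**Conclusion.** The point holds as a minor efficiency and consistency matter. The care-process, CTM-15 and change-score comparisons ignore strata that the plan uses for PORT delay and time to PORT. The tests are valid, and conservative to the extent that race or facility predicts the endpoint.

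Stratifying gains about 0 to 3 points of power for facility gaps of up to 30 points, and 6 to 11 points at gaps of 40 to 50 points. These figures assume an even facility split, alpha 0.05, about 75 analysed per arm, and the stated gaps and effects, none of which the documents give for these endpoints. The conclusion does not depend on whether 4.2.1 or 6.3 describes the randomisation correctly, since both aim to balance race and facility across arms.

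**What to change.** In 9.4.3.2:
- Compare the six binary care-process endpoints by the Mantel-Haenszel test with the primary endpoint's strata, using an exact stratified version for sparse counts such as dental extractions. Report a stratified risk difference with its confidence interval.
- Compare CTM-15, which the schedule of activities places at Visits 3 and 4 with no baseline, and the change scores by van Elteren tests or stratum-adjusted linear models on the same strata. Fix the choice between the two in advance.

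In 4.2.1 and 6.3, reconcile whether race is a randomisation stratum or a sampling stratum, so that the strata in the analysis are unambiguous.

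The cost is a few sentences and a little programming. It needs no new data and no change to the sample size or the primary analysis.
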